8.1 Missing Data

Missing data occurs when any requested data are not provided, leading to blank fields on the collection instrument. These data will be indicated by the use of a “blank” in by-subject listing displays. Answers such as “Not applicable” and “Not evaluable” are not considered to be missing data and should be displayed as such.

Because of the design and duration of the study, missing data are inevitable. The details of handling missing data are presented in the corresponding sections of this SAP for respective analyses (eg, primary and secondary endpoints, safety analyses).

8.2 General Derived Variables

8.2.1 Reference Dates and Study Days

Reference dates are used to assign study periods relative to treatment ([Section 8.4](#)).

- The safety reference date is the treatment start date, and will be used to calculate study day for safety measures.

The respective study day will be calculated as (date of interest - reference date) + 1 if the date of interest occurs on or after the reference date. If the date of interest occurs before the reference date, then the study day will be calculated as (date of interest – reference date). There will be no study day zero.

8.2.2 Durations

Durations (eg, the duration of an AE) are calculated in days as:

- Event end date – event start date + 1, if end time or start time not available;
- Event end date / time – event start date / time, if both end time and start time available.

Thus, there will be no duration of 0 if end time or start time are not available. If an AE has missing or partially missing start or end date, no duration will be calculated.

To transform durations or elapsed times, which are calculated in days into weeks, divide the number of days by 7; to report in months, divide the number of days by 30.4375; to report in years, divide the number of days by 365.25. These algorithms return decimal numbers, and ignore the actual numbers of days in the months or years (the calendar days) between start date and stop date. The "year" used in these algorithms is 365.25 days long, and the "month" is one-twelfth of that year.

8.2.3 Baseline Definition

Baseline is defined as the most recent, non missing value before the first IP administration (including unscheduled visits) for all assessments unless otherwise stated.

8.2.4 Change from Baseline

Change from baseline is calculated as:

- Visit value – baseline value.

Percentage change from baseline is calculated as:

- (Change from baseline / baseline value) * 100.

The percent of baseline is calculated as:

- (Visit value / baseline value) * 100.

If either the baseline or visit value is missing, the change and percent change from baseline is missing.

8.2.5 Multiple Assessments

All data will be reported according to the nominal visit date for which they were reported (that is, no visit windows will be applied during dataset creation and the visit will not be re-allocated if the actual visit date deviates from the planned date according to the visit schedule in the protocol). Unscheduled data will not be included in by-visit summaries, but will appear chronologically in by-subject listing. Data from all assessments (scheduled and unscheduled), including multiple assessments, will be included in by-subject listing.

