ADA = antidrug antibody; AE = adverse event; ALT= alanine aminotransferase; aPTT = activated partial thromboplastin time; AST = aspartate aminotransferase; BMI = body mass index; CCL = C-C motif chemokine ligand; CK = creatinine kinase; CPa9-HNE = neo-epitope of calprotectin generated by human neutrophil elastase; CPK = creatinine phosphokinase; CRPM = neo-epitope of matrix metalloproteinase-mediated degradation of C-reactive protein; CSL = CSL Behring; CXCL = C-X-C motif chemokine ligand; DL_{CO} = diffusing capacity of the lungs for carbon monoxide; ECG = electrocardiogram; EOI = end of the infusion; EOT = end of treatment; EW = early withdrawal; FU = follow-up; GGT = gamma glutamyltransferase; HDL = high-density lipoprotein; hs-CRP = high-sensitivity C-reactive protein; IPF = idiopathic pulmonary fibrosis; IL=interleukin; INR = international normalized ratio; IRT = interactive response technology; IV = intravenous; LDH= lactate dehydrogenase; LDL = low-density lipoprotein; MCH = mean corpuscular hemoglobin; MCHC = mean corpuscular hemoglobin concentration; MCV = mean corpuscular volume; PAI-1 = plasminogen activator inhibitor 1; PD = pharmacodynamic; pF1+2 = prothrombin fragment; PFT = pulmonary function test; PK = pharmacokinetic; Pro-Fib = biomarker specifically targeting the thrombin-mediated conversion of fibrinogen into fibrin; PT = prothrombin time; RBC = red blood cell; RDW = red cell (erythrocyte) distribution width; RNA seq = ribonucleic acid sequencing; SC = subcutaneous; SP-A = surfactant protein A; SP-D = surfactant protein D; TN-C = tenascin-C; TSP-1 = thrombospondin 1; VEGF = vascular endothelial growth factor; VICM = neo-epitope of matrix metalloproteinase-mediated degradation of citrullinated vimentin; WBC = white blood cell.

Notes for the Schedule of Assessments:

- A. Eligible subjects must discontinue all prohibited medications \geq 28 days (or 5 half-lives) before randomization.
- B. The Follow-up Visit will be a telephone call conducted on Day 154 (\pm 5), approximately 90 days after the last administration of investigational product, to collect data on AEs (including acute exacerbations of IPF) and concomitant medications since the previous study visit.
- C. EOT / EW Visit. If a subject withdraws from the study before the Week 14 Visit, the subject will be asked to return to the study site to complete the EOT assessments.

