4.3 Discontinuation of Study Treatment and Subject Withdrawal

4.3.1 Discontinuation of Study Treatment

Subjects may discontinue study treatment with investigational product at any time at their own request, or at the discretion of the investigator or CSL for safety, behavioral, or administrative reasons.

Subjects who discontinue treatment with investigational product but remain in the study, will be asked to complete additional follow-up assessments or allow data collection as detailed in the [Schedule of Assessments](#). If a subject discontinues investigational product and declines further study procedures / visit participation, the subject will be withdrawn from the study, and attempts will be made to complete and document the Withdrawal Visit assessments. Refer to Section 4.3.2 and Section 4.3.3 for details on handling subject withdrawals.

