4.3.3 Procedures for Handling Withdrawals

If a subject is withdrawn from the study, attempts will be made to complete and document the End-of-Treatment (EOT) Visit assessments. If the subject is withdrawn from the study after receiving investigational product, every effort will be made to ensure that the relevant safety assessments are completed. The subject may also be asked by the investigator to complete other study assessments.

If the subject withdraws from the study, and also withdraws consent for disclosure of future information, CSL may retain and continue to use any data collected before such withdrawal of consent.

Publicly available records will be used to establish the vital status of subjects who withdraw from the study and withdraw consent for disclosure of future information.

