As a safety parameter, single-breath DL_{CO} will be assessed at Screening, before administration of investigational product on Day 1 (Baseline), and at Week 14 (EOT / EW Visit). DL_{CO} will be assessed at the study site by the investigator or a qualified designee according to the site's SOPs, and conducted in accordance with criteria published by ATS / ERS [Graham et al, 2017]. The DL_{CO} reference ranges used will be those established by the Global Lung Function Initiative [Stanojevic et al, 2017]. DL_{CO} will be corrected for hemoglobin retrospectively using a blood sample collected on the same day as the DL_{CO} measurement, if available.

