8.5.5 End-of-Treatment Visit

The scheduled end of study participation for an individual subject occurs with completion of the EOT Visit on Day 92 ± 2 days, after which no further study-related procedures will be performed.

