8.5.7 Withdrawal

If a subject is withdrawn from the study before the Week 14 Visit (EOT Visit), the investigator should make every effort to perform the assessments during the subjects last study visit or, if possible, encourage the subject to return to the study site for EOT assessments.

9 Adverse Events

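### SAP 8.2.5 makes no exception for early withdrawal, so unless the eCRF labels such visits separately, a dropout's early values would be analysed as Day 92

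*SAP*

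**What the plan says.** **Protocol.** The Schedule of Assessments has a single EOT/EW column at Week 14, Day 92. Note C says that if a subject withdraws before Week 14, "the subject will be asked to return to the study site to complete the EOT assessments". Section 8.1.5 uses the same combined name for DLCO, which is measured at Screening, "before administration of investigational product on Day 1 (Baseline), and at Week 14 (EOT / EW Visit").

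The naming elsewhere is mixed:
- Section 4.3.1: "attempts will be made to complete and document the Withdrawal Visit assessments", with a pointer to 4.3.3.
- Section 4.3.3: "attempts will be made to complete and document the End-of-Treatment (EOT) Visit assessments".
- Section 8.5.5: scheduled participation "occurs with completion of the EOT Visit on Day 92", with a window of ±2 days.
- Section 8.5.7: "the investigator should make every effort to perform the assessments during the subjects last study visit", or else bring the subject back for the EOT assessments.

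**SAP.** Section 8.2.5 allocates by nominal visit: "no visit windows will be applied during dataset creation and the visit will not be re-allocated if the actual visit date deviates". Unscheduled results are kept out of by-visit summaries. Early withdrawal is not mentioned. Section 13.1 names Day 92 as the time point of main interest for kallikrein activity. Section 13.2.1 takes the FVC decline counts and the correlations at Day 92 and plans no imputation of missing FVC. Section 11.3 tells the analyst what to do when a dropout lacks a Day 92 value, but only for laboratory shift tables.

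**The concern.** Taken together, the rule and the combined visit turn an early value into a Day 92 value. A subject who withdraws on Day 40 and returns for the EOT assessments would have those results entered at EOT/EW, and SAP 8.2.5 then forbids moving them. The result reflects less follow-up and possibly fewer doses.

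The analyses reached are the mixed models for kallikrein activity (the secondary PD endpoint), other PD measures, biomarkers and FVC; the counts of subjects with FVC decline of at least 5% or 10%; the Day 92 correlation plots; the DLCO summary; and the nominal-time concentration summaries. The FVC model is meant to treat a visit after withdrawal as missing. Filing the early value there replaces that with something close to last observation carried forward, which the SAP nowhere chooses. DLCO is the plainest case, because its only scheduled post-baseline measurement is at EOT/EW.

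**Working it through.** **The plan's own figure.** 70 / (1 − 0.12) = 79.5, so about 80 enrolled; forward, 80 × 0.88 = 70.4. The stated 80 and 70 reproduce. Expected dropouts: 80 × 0.12 = 9.6.

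**FVC, equal dropout.** The documents give no withdrawal dates, return rates or FVC standard deviation. I assume linear change from Day 1 to Day 92, withdrawal uniform over Days 15 to 85, and every returning dropout filed at Day 92.
- Mean withdrawal day 50; elapsed fraction 49/91 = 0.538; shortfall 0.462.
- All return: EW share of Day 92 values 0.120; shrinkage 0.120 × 0.462 = 5.5%.
- Half return: share 0.06/0.94 = 0.0638; shrinkage 0.0638 × 0.462 = 2.9%.
- In standard errors, for an assumed 0.5-SD effect and 35 per arm: 0.0554 × 0.5 / √(2/35) = 0.12, and 0.0295 × 0.5 / √(2/35) = 0.06.

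**FVC, all withdrawals on one day.** With 10 of 80 records early (80 − 70 = 10), shrinkage is (10/80) × (1 − (t − 1)/91). With half returning, the share is 5/75.

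| EW day t | All return | Half return |
|---|---|---|
| 15 | 10.6% | 5.6% |
| 36 | 7.7% | 4.1% |
| 64 | 3.8% | 2.1% |

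**FVC, unequal dropout.** Assume 2 of 40 in one arm and 8 of 40 in the other, all returning, and no true effect. The spurious difference, as a fraction of the 14-week decline, is (8/40 − 2/40) × (1 − (t − 1)/91): 12.7% at Day 15 and 4.6% at Day 64. The arm with more dropouts looks as if it declined less.

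**Kallikrein activity.** I assume a one-compartment model with half-life 18 days and Tmax 7 days (Protocol 1.2.3.1), which gives an absorption rate of 0.356 per day; bioavailability 0.5 (Protocol 3.3.2); and the planned doses on Days 1, 8, 36 and 64. With r = C(t)/C(92), inhibition is r/(r + 1/9), which gives 90% at Day 92, in line with the projection in Protocol 3.3.2. Over Days 15 to 85:

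| | r, range (mean) | Mean shift per misfiled subject | Group mean, all return (× 0.12) | Group mean, half return (× 0.0638) |
|---|---|---|---|---|
| Due doses given | 1.02–2.30 (1.69) | +3.57 points | +0.4 | +0.2 |
| Latest due dose missed | 0.37–1.05 (0.68) | −4.90 points | −0.6 | −0.3 |

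Single-day extremes with all returning: +5.4 × 0.12 = +0.6 (Day 15, doses given) and −13.0 × 0.12 = −1.6 (Day 64, Day 36 dose missed).

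**After the change proposed under fix.** No withdrawal on Days 15 to 85 falls inside Days 90 to 94, so under these assumptions the contamination of Day 92 is zero. Day 92 then rests on about 70 subjects, the number the plan already calls evaluable.

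**The case against.** **The label is unknown.** SAP 8.2.5 works on the visit at which data are reported, so the eCRF decides. A reader might infer that the SAP certainly analyses early values as Day 92. The documents do not support that. The eCRF may have a separate withdrawal visit, as the wording of Protocol 4.3.1 could suggest, and values logged as unscheduled or at the last attended visit (Protocol 8.5.7) are not misfiled. This stands, and the point is conditional on it.

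**Other SAP text points the other way.** Section 11.3 speaks of dropouts without a Day 92 value, Section 9.1 separates Day 92 completers from earlier discontinuations, and the evaluable number is net of dropout. All this fits dropouts lacking Day 92 data. But Section 11.3 governs only laboratory shift tables, and neither document describes a separate EW label or a mapping rule. The intention may be right; the rule does not carry it out.

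**Keeping the early values may be more precise.** With equal dropout, all returning and a 0.5-SD effect, filing them at Day 92 gives a mean squared error of 2/40 + 0.0277² = 0.0508 SD². Leaving them missing gives 2[(1 − r²)/35.2 + r²/40], where r here is the assumed correlation of Day 64 with Day 92: 0.0535 at r = 0.7 and 0.0525 at r = 0.8, breaking even near r = 0.94. The arithmetic is right, but it assumes equal dropout by arm and so omits the bias shown above for unequal dropout. It does support a sensitivity analysis that keeps all the values.

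**Conclusion.** The point holds conditionally. On the natural reading of the two documents, an EW value entered at EOT/EW is analysed as Day 92; a separate eCRF label would remove the problem, but the SAP should say so.

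The size is small: about 3% to 6% attenuation of the Day 92 FVC difference, or 0.06 to 0.12 standard error, under the assumed equal 12% dropout, linear change and uniform withdrawal. For kallikrein activity the average shift is within about 0.6 points in either direction. Dropout that differs by arm could do more or create a difference where none exists, so the direction cannot be stated in advance.

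A reader might also infer that the primary safety results or the PK parameters are distorted. They are not: adverse events are classified by date, and the non-compartmental parameters use actual times and doses (SAP 12.2). Nor does this undermine a trial conclusion. There is no primary hypothesis (SAP 4.1.1), p-values are nominal (Protocol 10.3.1) and FVC is exploratory. It is a cheap improvement.

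**What to change.** Add one exception to SAP 8.2.5, covering the PD, biomarker, FVC, DLCO and nominal-time concentration analyses:

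1. An EW assessment counts as Day 92 only if its actual study day lies within the protocol's Day 92 ± 2 window.
2. If it lies within the protocol window of another visit at which that assessment is scheduled, and that visit has no value, it may be used there.
3. Otherwise it gets a separate EW analysis visit: listed, and for DLCO also summarised on its own row. Day 92 stays missing for the mixed models, decline counts and correlations.

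Apply the same rule to every one of these measures, so that the paired Day 92 plots stay aligned.

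Leave the safety analyses unchanged: adverse events, antidrug antibodies at any time, ECG, vital signs, and the last-observed laboratory rule in SAP 11.3, which may still use EW values. Keep on-schedule Day 92 values from those described in Protocol 4.3.1 as "Subjects who discontinue treatment with investigational product but remain in the study". Add one sensitivity analysis that counts all EW values as Day 92.

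**Cost.** One SAP paragraph, one derivation step and one extra run; SAP 9.1 already lists withdrawal dates. The SAP cites the protocol only through Amendment 2 and the protocol is now at Amendment 3, so a revision is a natural occasion. The downside is up to about 9.6 fewer Day 92 values than under literal filing, and reliance on missing-at-random in the main model. A value moved off Day 92 may be the worst FVC of a subject leaving for progression, which is why the sensitivity analysis is needed.

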8.2.6 Actual Treatment

The subjects' actual treatment will be derived from exposure data. If a subject receives a study treatment that is different from the planned treatment for the entire time of treatment, then actual treatment is the treatment actually received. In the event that a subject receives both CSL312 and placebo, the subject will be included in the CSL312 group for this analysis set. Subjects receiving only placebo will be included in the placebo group.

8.3 Stratification

The study design does not include any stratification factors. There are no formal plans for investigating any covariates.

8.4 Study Periods Relative to Treatment

All data will be assigned to 1 of the 3 study time periods defined below.

- **Pre treatment** is defined as the time before the subject's first date / time of IP (Day 1).
- **On-treatment** (Treatment and Observation Period) is defined as the time from first date / time of IP up to Week 14 (Day 1 to Day 92).
- **Post treatment** begins after the end of the Treatment and Observation Period (Day 92) and continues through the Follow-up visit (follow-up telephone call) (Day 154).

9 Study Population

Unless otherwise stated, all tables and listings in this section will be based on the Safety Analysis Set.

9.1 Subject Disposition

The following summaries will be provided for the Screened Analysis Set by CSL312 group, placebo group, and total population for:

- Subjects who underwent Screening – only total;
- Subjects who are re screened – only total;
- Screening failures with reason for failure – only total;
- Subjects eligible for randomization – only total;
- Subjects randomized – by treatment and total;
- Subjects randomized but not treated – by treatment and total;
- Subjects treated – by treatment and total;
- Subjects treated who completed treatment through Day 64 – by treatment and total;
- Subjects treated who completed the Treatment and Observation Period (Day 92) – by treatment and total;
- Subjects treated who discontinued from the study before end of treatment (Day 64) with reason (including discontinuation due to COVID-19) – by treatment and total;

- Subjects treated who discontinued from the study before end of Treatment and Observation Period (Day 92) with reason (including discontinuation due to COVID-19) – by treatment and total;
- Subjects treated who completed the study through the Follow-up Visit – by treatment and total;
- Subjects treated who discontinued from the study before the Follow-up Visit with reason (including discontinuation due to COVID-19) – by treatment and total;
- Subjects in each of the analysis sets described in [Section 6](#).

Reasons for study withdrawal and study treatment discontinuation will be presented in the order they are displayed in the eCRF.

By-subject listing will be provided for disposition status for each subject. This will include:

- Randomization scheme based on the randomized treatment;
- Subjects treatment used in safety analysis;
- Subject disposition with date of screening (in case of re-screening, all screening records will be listed), date (and time) of randomization, date (and time) of first IP administration, date of completion of / or withdrawal from the Treatment and Observation Period, and date of study completion or withdrawal from the study;
- Screening failures with the reason;
- Subjects who discontinued from study treatment with the reason for discontinuation and subjects who discontinued from the study with the reason for discontinuation;
- Subject assignment to analysis sets and reasons for exclusion.

9.2 Protocol Deviations

A protocol deviation occurs when an investigator site, or study subject, does not adhere to protocol-specified requirements. Deviations will be assessed by CSL Behring as they are reported and then evaluated periodically during study conduct, based on the protocol deviation plan for this study developed by CSL Behring.

Deviations will be categorized as either major or minor. Major protocol deviations for subjects in the Safety Analysis Set will be summarized for number and percentage of subjects with each protocol deviation, though all major and minor deviations will be listed. The summary will be given by treatment group and overall.

The final decision regarding protocol deviations and assignment of subjects to analysis population will be made during the blinded data review meeting.

A by-subject listings will be provided based on the Safety Analysis Set covering the following information:

- All protocol deviations (including inclusion and exclusion criteria violations).

9.3 Demographic and Baseline Characteristics

Descriptive statistics as specified in [Section 7](#) will be provided for continuous variables, number and percentage of subjects for categorical variables.

The following summaries will be provided for the Safety Analysis Set by treatment group and overall:

- Demographic characteristics (eg, age, race, ethnicity, sex, smoking history, baseline height, and baseline body weight, and body mass index (BMI)). In addition to summarization as a continuous variable, age will also be categorized and summarized by ≥ 40 to ≤ 64 years, ≥ 65 to ≤ 74 years, ≥ 75 to ≤ 84 years and ≥ 85 years;
- Disease characteristics including the duration since IPF diagnosis and previous treatment with nintedanib or pirfenidone, baseline FXIIa-mediated kallikrein activity, baseline absolute and percent predicted in FVC;
- Medical history (coded using MedDRA – the MedDRA version will be populated in the outputs) will be presented by SOC and preferred term.

Corresponding by-subject listings will be provided. The by-subject listing for disease characteristics will include but is not limited to the year of diagnosis as well as the duration of IPF. The medical history by-subject listing will also provide an indicator of whether the condition was active at the time of entry into the screening period.

Nonpharmacological procedures will only be presented in a by-subject listing.

